8.3.3.3 EXPECTEDNESS

The PI will be responsible for determining whether an adverse event (AE) is expected or unexpected. An AE will be considered unexpected if the nature, severity, or frequency of the event is not consistent with the risk information previously described for the study intervention.

8.3.4 TIME PERIOD AND FREQUENCY FOR EVENT ASSESSMENT AND FOLLOW-UP

The occurrence of an adverse event (AE) or serious adverse event (SAE) may come to the attention of study personnel during study visits and interviews of a study participant presenting for medical care, or upon review by a study monitor.

All AEs including local and systemic reactions not meeting the criteria for SAEs will be captured on the appropriate case report form (CRF). Information to be collected includes event description, time of onset, clinician's assessment of severity, relationship to study product (assessed only by those with the training and authority to make a diagnosis), and time of resolution/stabilization of the event. All AEs occurring while on study must be documented appropriately regardless of relationship. All AEs will be followed to adequate resolution.

Any medical condition that is present at the time that the participant is screened will be considered as baseline and not reported as an AE. However, if the study participant's condition deteriorates at any time during the study, it will be recorded as an AE.

Changes in the severity of an AE will be documented to allow an assessment of the duration of the event at each level of severity to be performed. AEs characterized as intermittent require documentation of onset and duration of each episode.

Drs. [name], [name], [name], or [name] will record all reportable events with start dates occurring any time after informed consent is obtained until 7 (for non-serious AEs) or 30 days (for SAEs) after the last day of study participation. At each study visit, the investigator will inquire about the occurrence of AE/SAEs since the last visit. Events will be followed for outcome information until resolution or stabilization.

8.3.5 ADVERSE EVENT REPORTING

[name] will be responsible for reporting AEs to and following the guidance of any other applicable oversight bodies, including (but not limited to) the Institutional Review Board, the Data Safety and Monitoring Board, and the sponsor (the Icahn School of Medicine at Mount Sinai). At six-month intervals during the course of the study and again at its completion, the DSMB will be provided with summaries of the numbers and rates of adverse events. These reports will include types of events, severity, and treatment phase. Data on individual non-serious adverse events is not expected to be needed for this review.

Many subjects may admit to fleeting thoughts of death or briefly wishing for death; these thoughts need to be considered in context of the subject's overall history, along with a consideration of other risk factors for suicide. The presence of suicidal ideation without intent will therefore not be considered an Adverse Event, unless the suicidal ideation has increased in frequency or severity since baseline.

8.3.6 SERIOUS ADVERSE EVENT REPORTING

The study clinician will immediately report to the sponsor any serious adverse event, whether or not considered study intervention related, including those listed in the protocol or investigator brochure and must include an assessment of whether there is a reasonable possibility that the study intervention caused the event. Study endpoints that are serious adverse events (e.g., all-cause mortality) must be reported in accordance with the protocol unless there is evidence suggesting a causal relationship between the study intervention and the event (e.g., death from anaphylaxis). In that case, the investigator must immediately report the event to the DSMB and ISMMS IRB.

All serious adverse events (SAEs) will be followed until satisfactory resolution or until the site investigator deems the event to be chronic or the participant is stable. Other supporting documentation of the event may be requested by the DSMB or ISMMS IRB and should be provided as soon as possible.

The study sponsor (ISMMS) will be responsible for notifying the Food and Drug Administration (FDA) of any unexpected fatal or life-threatening suspected adverse reaction as soon as possible, but in no case later than 7 calendar days after the sponsor's initial receipt of the information.

8.3.7 REPORTING EVENTS TO PARTICIPANTS

Both ketamine and WET have been extensively used in clinical trials and clinical practice, thus AEs associated with these treatments are known; they are summarized in the study consent form, and are reviewed with study participants during administration of study consent procedures. In the event that

any unexpected AE emerges during the course of the study, this unexpected AE will be added to the study consent (through an IRB amendment request), and reviewed with study participants during consent procedures.

8.3.8 EVENTS OF SPECIAL INTEREST

Not applicable.

8.3.9 REPORTING OF PREGNANCY

In the event that a participant becomes pregnant while completing the study intervention(s), the participant will be exited from the trial after having completed end-of-infusion safety labs. Any pregnancies that occur while a subject is active in the protocol and after they have received ketamine infusions will be reported to the DSMB, ISMMS IRB, and other agencies (FDA, OHRP) as necessary.

8.4 UNANTICIPATED PROBLEMS

8.4.1 DEFINITION OF UNANTICIPATED PROBLEMS (UP)

The Office for Human Research Protections (OHRP) considers unanticipated problems involving risks to participants or others to include, in general, any incident, experience, or outcome that meets all of the following criteria:

- Unexpected in terms of nature, severity, or frequency given (a) the research procedures that are described in the protocol-related documents, such as the Institutional Review Board (IRB)-approved research protocol and informed consent document; and (b) the characteristics of the participant population being studied;
- Related or possibly related to participation in the research (“possibly related” means there is a reasonable possibility that the incident, experience, or outcome may have been caused by the procedures involved in the research); and
- Suggests that the research places participants or others at a greater risk of harm (including physical, psychological, economic, or social harm) than was previously known or recognized.

8.4.2 UNANTICIPATED PROBLEM REPORTING

The investigator will report unanticipated problems (UPs) to the reviewing Institutional Review Board (IRB). The UP report will include the following information:

- Protocol identifying information: protocol title and number, PI's name, and the IRB project number;
- A detailed description of the event, incident, experience, or outcome;
- An explanation of the basis for determining that the event, incident, experience, or outcome represents an UP;
- A description of any changes to the protocol or other corrective actions that have been taken or are proposed in response to the UP.

To satisfy the requirement for prompt reporting, UPs will be reported using the following timeline:

- UPs that are serious adverse events (SAEs) will be reported to the IRB within 24 hours of the investigator becoming aware of the event.
- Any other UP will be reported to the IRB within 5 business days of the investigator becoming aware of the problem.
- All UPs should be reported to appropriate institutional officials (as required by an institution's written reporting procedures), the supporting agency head (or designee), and the Office for Human Research Protections (OHRP) within 6 months of the IRB's receipt of the report of the problem from the investigator.

8.4.3 REPORTING UNANTICIPATED PROBLEMS TO PARTICIPANTS

Unanticipated problems will be added to the study consent form if any are identified (via an IRB amendment). Newly enrolled participants will thus be informed about any such problems during administration of consent procedures for the study.

9 STATISTICAL CONSIDERATIONS

9.1 STATISTICAL HYPOTHESES

- Primary Efficacy Endpoint(s):
 - The primary outcome is change in PTSD symptom severity from baseline to 12 weeks from the start of WET measured by the Clinician-Administered PTSD Scale for DSM-5 (CAPS-5) score at 12 weeks from the start of WET minus the CAPS-5 score at baseline. The analysis of the primary endpoint for this pilot study will be descriptive and no formal hypothesis testing will be conducted. The mean change in CAPS-5 score and corresponding 95% confidence interval will be reported.

- Secondary Efficacy Endpoint(s) (Exploratory):

In this early-phase study, analyses of secondary efficacy outcomes will be considered exploratory and hypothesis-generating. Therefore, no formal hypothesis testing will be conducted.

9.2 SAMPLE SIZE DETERMINATION

In this pilot study up to 15 patients will be enrolled. A sample size of 15 patients will produce a two-sided 95% confidence interval around the mean change in CAPS-5 at 12 weeks from the start of WET with a distance from the mean to the limits that is equal to 0.5 standard deviations.

Precision was calculated using PASS 2019.⁸³

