9.4 STATISTICAL ANALYSES

9.4.1 GENERAL APPROACH

Continuous variables will be summarized using the following descriptive statistics: number of non-missing values, means, standard deviations, medians, interquartile range, maximum, and minimum. Categorical variables will be summarized using number of non-missing values, counts and percentages.

Rates of events will be calculated as the ratio of the total number of events recorded divided by the total patient-time. Total patient-time will be calculated by summing the time (in study time units, e.g., days or months) that patients were at risk for a specific event from the reference time point until either study exit or the end of the time period of interest. Rates and their 95% confidence intervals will be reported.

Time-to-event variables will be summarized using the Kaplan-Meier method.

For any variable measured at multiple points in time, change since the day prior to starting WET, “pre-WET” (i.e., the day when response to ketamine is assessed), will be calculated as the difference between the value of the variable at a specific point in time (e.g. 12 weeks) minus the value from pre-WET. Relative change from pre-WET will be calculated as the value of a parameter at a specific point in time minus the pre-WET value of the parameter divided by the pre-WET value of the parameter. Percent change will be calculated as the relative change multiplied by 100.

Should any of the statistical methods proposed prove unsuitable during data analysis, more appropriate methods will be used. These include data transformation (for example to a logarithmic scale) to satisfy model assumptions such as normally distributed residuals with constant variance, the application of non-parametric techniques or the use of a different link function or analytical/modeling technique. The SAP will be updated with the methods used and the justification for the change prior to data set and database lock.

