9.4.2 ANALYSIS OF THE PRIMARY EFFICACY ENDPOINT(S)

The primary outcome is change in PTSD symptom severity from baseline to 12 weeks from the start of WET measured by the Clinician-Administered PTSD Scale for DSM-5 (CAPS-5) score at 12 weeks from the start of WET minus the CAPS-5 score at baseline. The analysis of the primary endpoint for this pilot study will be descriptive. The mean change in CAPS-5 score from baseline with corresponding 95% confidence interval will be reported.

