9.4.3 ANALYSIS OF THE SECONDARY ENDPOINT(S)

- **Secondary Efficacy Outcomes (Exploratory):** In this early-phase study, analyses of secondary efficacy outcomes will be considered exploratory and hypothesis-generating. CAPS-5, PCL-5, MADRS, CGI and SDS scores will be collected weekly through 6 weeks after the start of WET from all

eligible participants, and thereafter until 12 weeks (up to weekly, as tolerated, ensuring assessment at the 12-week time point for all participants). All participants will be followed naturally for 12 weeks from the start of WET, in order to capture, descriptively, more gradual effects of WET and potential effects of the combination of ketamine + WET in all patients. Thereafter, they will be collected monthly through week 24 from start of WET or until loss of treatment response, for the subgroup of participants who demonstrate improvement on the CAPS-5 at the 12-week assessment. Aggregate scores prior to adding WET, during WET, and during the maintenance phase (weeks 3 onward) will be reported descriptively at each time point using the number observed, mean, standard deviation, median, and interquartile range. Individual patient trajectories on these measures will be plotted over time to explore treatment response and patterns in maintenance of response. Mean change in CAPS-5 scores from baseline and corresponding 95% confidence intervals, as well as the proportion of patients with $\geq 30\%$ improvement from baseline on the CAPS-5 will also be reported at each time point. In addition, linear mixed-effects models of these outcomes may be fit to compare mean scores over time. Mixed models will test for the inclusion of a random intercept for patient and fixed effects for week against a fixed intercept model using a likelihood ratio test after comparing each model fit statistic (i.e., Akaike information criterion, AIC) where the best fitting model is the model with the lowest corresponding AIC. Once fit is assessed, parameter interpretation will commence.

- **IES-R and QIDS-SR with past-24-hour recall** – collected only at baseline, before each ketamine infusion, 24 hours after the first infusion, and on the response to ketamine assessment day – will be examined descriptively.

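### Section 9.2 gives a 95% CI half-width of 0.5 SD for 15 patients; with the SD estimated from those same patients, the t-based half-width is 0.55 SD

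*Combined protocol and SAP*

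**What the plan says.** Section 9.2 sets the size of the study ("In this pilot study up to 15 patients will be enrolled") and supports it with one precision statement: "A sample size of 15 patients will produce a two-sided 95% confidence interval around the mean change in CAPS-5 at 12 weeks", counted from the start of WET, "with a distance from the mean to the limits that is equal to 0.5 standard deviations". It cites PASS 2019. It gives no numerical SD, does not say whether the SD was treated as known or estimated, and does not report the software setting.

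Section 9.1 says that the primary analysis "will be descriptive and no formal hypothesis testing will be conducted". Section 9.4.2 describes the primary result: "The mean change in CAPS-5 score from baseline with corresponding 95% confidence interval will be reported". It does not say how the interval will be computed. Section 9.4.1 lists the summaries to be taken from the trial data: "Continuous variables will be summarized using the following descriptive statistics: number of non-missing values, means, standard deviations", among others. No outside value for the SD of the 12-week change is supplied anywhere for use in the analysis.

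**The concern.** A half-width of 0.5 SD at n = 15 is what the normal formula gives when the SD is known. Nothing in the plan makes it known. With 14 degrees of freedom the t multiplier is 2.145 rather than 1.960, a difference large enough to change the first decimal of the half-width in sample-SD units.

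Because section 9.1 rules out hypothesis testing, there is no power calculation behind the 15 patients. The precision statement is the only quantitative reason given for the sample size, so it should describe the interval that will be reported. As written, it makes the pilot look slightly more precise than it will be.

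**Working it through.** **Inputs.** n = 15 and a two-sided 95% level (section 9.2); stated half-width 0.5 SD (section 9.2); a single-arm mean change with its 95% CI (section 9.4.2); SD taken from the trial data (section 9.4.1, with no external SD supplied).

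**1. Reproduce the stated figure, SD treated as known.** Half-width = z(0.975)/√n.
- n = 15: 1.960/3.873 = 0.506 SD, which is 0.5 to one decimal.
- Inverted: n = (1.960/0.5)² = 15.4, so 16 patients are needed for 0.5 or less (at n = 16 the half-width is 0.490).

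The figure is therefore not an arithmetic slip; it fits the known-SD formula.

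**2. SD estimated from the same patients.** Half-width in sample SDs = t(0.975, n−1)/√n.
- n = 15: 2.1448/3.8730 = 0.554
- n = 16: 0.533
- n = 17: 0.514
- n = 18: 0.497, the first value at or below 0.5

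Of the three patients between 15 and 18, one is due to rounding in the known-SD result itself (16 rather than 15).

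**3. The same t interval in units of the true SD, assuming normal changes.** The sample SD varies and is on average slightly below the true SD.
- Expected half-width at n = 15: 0.5538 × c4(15) = 0.544, where c4 is the ratio of the expected sample SD to the true SD
- Median half-width: 0.5538 × √(median of χ² on 14 df / 14) = 0.541
- Probability that the half-width is 0.5 true SD or less: about 35%

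**4. Size of the gap.**
- 0.5538/0.5061 = 1.094, so 9.4% wider than the known-SD value
- 0.5440/0.5061 = 1.075, so 7.5% wider on the expected value in true-SD units
- 0.5538/0.5 = 1.108, so about 11% wider than the printed 0.5

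**5. Coverage if 0.5 sample SD were used literally.** The mean ± 0.5 sample SD at n = 15 corresponds to a t statistic of 0.5 × √15 = 1.936 on 14 df, which gives 92.7% coverage under normality. The normal multiplier applied to the sample SD (half-width 0.506) gives 93.0%.

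**6. Fewer evaluable patients (illustrative counts only).** The documents give no expected missing rate at week 12, so 12 and 10 are assumptions. The t-based half-width is 0.635 SD with 12 patients and 0.715 SD with 10.

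**The case against.** The strongest reply is that the number is right to the precision at which it is printed. A planning statement made before any data exist is naturally read in population-SD units. On that reading the known-SD value (0.506), the expected t half-width (0.544) and the median t half-width (0.541) all round to 0.5. Only the sample-SD reading (0.554) rounds to 0.6. Section 9.2 does not say which SD it means, and the PASS setting cannot be seen, so nobody can show that the authors used an unsuitable method. Nor was 0.5 SD declared as a target, so the 18-patient figure answers a requirement that the plan never set. Section 9.4.2 does not suggest that a normal interval will be used, and section 9.4.1 allows methods to be changed with justification.

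Much of this stands. The known-SD formula is an acceptable planning convention when it is declared, the cause of the discrepancy is an inference, and the consequences are small. It does not rescue the wording. The text says that the distance equals 0.5 SD and attaches no condition. The SD has to come from the trial, and the t interval then has a half-width above 0.5 true SD in roughly two trials out of three.

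The illustrative counts of 12 and 10 bear on missing data, which is a separate matter, and section 9.4.3 commits to "ensuring assessment at the 12-week time point for all participants". Against that, 15 is a maximum, section 9.2 makes no allowance for loss, and section 7.2 does not replace treated participants who withdraw. The counts are useful context but not part of the error.

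**Conclusion.** The concern holds, as a minor point. The plan claims a half-width of 0.5 SD; the conventional t interval for 15 patients gives 0.554 sample SDs, or 0.544 expected in true-SD units. The claim is too favourable by about 0.05 SD.

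This rests on three assumptions: that the SD is estimated from the trial patients, that the reported interval is the usual t interval, and that all 15 patients contribute a 12-week value. The true-SD, probability and coverage results also assume normally distributed changes.

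No decision rule depends on 0.5 SD, and the published interval will be computed from the data whatever section 9.2 says. The analysis is not invalidated and the sample size need not change.

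**What to change.** Restate the precision in section 9.2, for example: *With 15 evaluable patients, the half-width of the two-sided 95% t-based confidence interval for the mean change in CAPS-5 is 0.55 SD, with the SD estimated from the sample.*

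Two optional additions would help the reader. Section 9.2 could add that the half-width would be 0.64 SD with 12 evaluable patients and 0.72 SD with 10, labelled as illustrative. Section 9.4.2 could state that the interval is based on the t distribution.

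The cost is wording only. The stated precision becomes slightly less favourable; enrolment, design and conduct are unchanged.

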9.3 POPULATIONS FOR ANALYSES

Analysis datasets will include and Intention-to-treat (ITT) Analysis Dataset (all enrolled patients) and a Per-protocol Analysis Dataset (including only participants who completed the study). Additionally, a Safety Analysis Dataset and descriptive analyses will include all participants in the study.

9.4 STATISTICAL ANALYSES

9.4.1 GENERAL APPROACH

Continuous variables will be summarized using the following descriptive statistics: number of non-missing values, means, standard deviations, medians, interquartile range, maximum, and minimum. Categorical variables will be summarized using number of non-missing values, counts and percentages.

Rates of events will be calculated as the ratio of the total number of events recorded divided by the total patient-time. Total patient-time will be calculated by summing the time (in study time units, e.g., days or months) that patients were at risk for a specific event from the reference time point until either study exit or the end of the time period of interest. Rates and their 95% confidence intervals will be reported.

Time-to-event variables will be summarized using the Kaplan-Meier method.

For any variable measured at multiple points in time, change since the day prior to starting WET, “pre-WET” (i.e., the day when response to ketamine is assessed), will be calculated as the difference between the value of the variable at a specific point in time (e.g. 12 weeks) minus the value from pre-WET. Relative change from pre-WET will be calculated as the value of a parameter at a specific point in time minus the pre-WET value of the parameter divided by the pre-WET value of the parameter. Percent change will be calculated as the relative change multiplied by 100.

Should any of the statistical methods proposed prove unsuitable during data analysis, more appropriate methods will be used. These include data transformation (for example to a logarithmic scale) to satisfy model assumptions such as normally distributed residuals with constant variance, the application of non-parametric techniques or the use of a different link function or analytical/modeling technique. The SAP will be updated with the methods used and the justification for the change prior to data set and database lock.

